We will measure male clients’ perceived utility and comprehension of text messages by asking clients to rate the extent to which the text messages were a) useful, b) enjoyable, and c) easy to understand. Questions will be on a 4-point Likert Scale and will be asked of clients at the end of each MB module (Introduction, Pleasant Activities, Thoughts, Contact with Others and Review/Conclusion). We will measure male and female clients’ perceived feasibility and acceptability post intervention. These data will be collected via REDCap.

Home Visitors: Home visitors will be asked to respond to a REDCap survey items after completing each MB session to assess if female clients came to the session having completed their personal project, implemented session, and next scheduled session date. Home visitors will measure female clients’ perceived utility and comprehension of text messages by asking clients to rate the extent to which each of the 3 text messages received between sessions was a) useful and b) easy to understand. Questions will be on a 4-point Likert Scale and will be asked of clients at the end of each MB session. These data will be inputted into the HealthySMS system. We will assess home visitors’ perceived feasibility and acceptability post intervention after all 12 session of MB-TXT and FAB are completed.. These data will be collected via REDCap.

Focus Groups: There will be three focus groups and 4 key informant interviews during the study and will take place during phase 2 after participants have completed FAB. All focus group and key informant participants will receive \$35 remuneration in the form of a Northwestern PNC stored-value card (Visa Gift-Card).

Table 1: Detailed Description of Study Measures for Phase1

Text messages read by HV clients will be measured by calculating the percentage of text messages responded to by clients.
Home Visitor Adherence to MB-TXT protocol will be measured by using the archived data from HealthySMS to calculate the percentage of texts sent at the appropriate intervals, as stated in the MB Instructor Manual
Client completion of personal projects will be measured by asking home visitors to respond to a REDCap survey item after completing each MB session to assess if clients came to the session having completed their personal project.
Client perceived utility and comprehension of text messages will be measured by asking home visitors to rate the extent to which each of the 3 text messages received between sessions was a) useful and b) easy to understand. Questions will be on a 4-point Likert Scale and will be asked of clients at the end of each MB session. These data will be inputted into REDCap.
Depressive Symptoms will be assessed using the Beck Depression Inventory-II (BDI), ¹⁰⁰ a 21-item self-report measure of depressive symptoms to assess severity of depressive symptoms consistent with DSM-IV symptom criteria. The BDI has excellent internal reliability for outpatient samples and its construct validity has been established.
Cognitive Structuring will be measures using the Experiences Questionnaire ⁸⁵ a 20-item self-report scale measuring decentering and rumination, which has demonstrated strong internal consistency in studies examining effects of interventions that incorporate cognitive restructuring.
Behavioral Activation will be measured using the Behavioral Activation Depression Scale, ⁸⁶ a 25-item, four subscale self-report with strong psychometric properties. ^{86,87} The four subscales assess activation, avoidance/rumination, work/school impairment, and social impairment. We will also use a brief checklist adapted from the Pleasant Events Schedule, a psychometrically strong questionnaire. ⁸⁸ This 25 item self-report contains a list of pleasant events relevant to low-income pregnant women and assesses the extent to which subject’s engaged in, and experienced pleasure from, these activities.

Social Support using the 19-item Medical Outcomes Study Social Support Survey.⁸⁹ This self-administered survey includes an overall functional social support index, as well as four functional support subscales: affectionate, emotional/informational, tangible, and positive social interaction.


Mood regulation will be measured using the Negative Mood Regulation Scale (NMRS).⁹⁰ The NMRS assesses an individual’s expectancy that some behavior or cognition will alleviate a negative mood state. For each question, respondents use a five-point scale from “very much disagree” to “very much agree” to indicate what they believe they can do when they are disappointed or experiencing a negative mood. The scale has demonstrated excellent internal consistency, good test-retest reliability, and correlational evidence of both convergent and discriminant validity with constructs such as depressive symptoms and locus of control, respectively.⁹¹

Mothers and Babies Skill Utilization will be assessed using items developed the study investigators.

Client demographics will be assessed using items developed by the study investigators. Baseline Demographics –17 items 3 & 6 month Follow-up Demographics – 8 items

Prenatal Behavior and Service Utilization. - will be assessed using items developed by the study investigators.

Table 2: Detailed Description of Study Measures for Phase 2

Text messages read by HV clients will be measured by calculating the percentage of text messages responded to by female and male study participants.

Home Visitor Adherence to MB-TXT protocol will be measured by using the archived data from HealthySMS to calculate the percentage of texts sent at the appropriate intervals, as stated in the MB Instructor Manual.

HV Post Intervention Survey will be assessed using questions developed by the study investigators. Questions will be on a 4-point Likert Scale and will be asked of home visitors at the end of the 12 MB sessions.

Female Client perceived utility and comprehension of text messages will be measured by asking home visitors to rate the extent to which each of the 3 text messages received between sessions was a) useful and b) easy to understand. Questions will be on a 4-point Likert Scale and will be asked of clients at the end of each MB session. These data will be inputted into HealthySMS.

Female Client Post Intervention Survey will be assessed using questions developed by the study investigators. Questions will be on a 4-point Likert Scale and will be asked of the female clients at the end of the 12 MB sessions.


Male Partner perceived utility and comprehension of text messages will be measured by a survey to rate the extent to which the text messages received were a) useful and b) easy to understand. Questions will be on a 4-point Likert Scale and will be asked of clients at the end of each MB module.

Male Partner Post Intervention Survey will be assessed using questions developed by the study investigators. Questions will be on a 4-point Likert Scale and will be asked of male partners at the end of the 12 MB sessions.

Depressive Symptoms will be assessed using the Beck Depression Inventory-II (BDI),¹⁰⁰ a 21-item self-report measure of depressive symptoms to assess severity of depressive symptoms consistent with DSM-IV symptom criteria. The BDI has excellent internal reliability for outpatient samples and its construct validity has been established.

Anxiety symptoms will be assessed using the GAD-7- To assess anxiety, we will administer the Generalized Anxiety Disorder 7-item scale (GAD-7; Spitzer et al., 2006), which is a widely used self-report measure of anxiety symptoms.

Perceived stress will be assessed using the Perceived Stress Scale 10-item version. We will use the 10-item Perceived Stress Scale (PSS-10; Cohen & Williamson, 1988; Remor et al., 2006) to assess the level to which an individual considers their life stressful and how controllable a

person appraises her life.

Social Support will be assessed using the NIH Toolbox Instrumental Support and Emotional Support measures. Each measure asks 8 questions and asks respondents to indicate the extent to which they have received support for each area in the last month.

Mothers and Babies Skill Utilization will be assessed using items developed the study investigators.

Client demographics will be assessed using items developed by the study investigators. Female Client Baseline Demographics- 18 items Female Client 3 & 6 Follow-Up Demographics- 10 items Male Partner Baseline Demographics – 14 items Male Partner 3 & 6 Follow-Up Demographics- 8 items

Prenatal Behavior and Service Utilization. - will be assessed using items developed by the study investigators.


Relationship with partner will be measured using the Revised Dyadic Adjustment Scale (RDAS) cohesion subscale. The RDAS cohesion subscale is most relevant to this study and measures items such as engaging in activities together. The cohesion subscale consists of 4 items, each of which asks respondents to rate certain aspects of his/her relationship on a 5- or 6- point scale. Higher scores indicate greater relationship satisfaction. The RDAS has demonstrated excellent internal consistency.⁹⁷

Fathers' involvement with child will be measured using the 10-item Father Engagement Scale (Dyer et al., 2015) which measures the number of times per month fathers engage in different types of activities with their child.

Perceived social support from partner will be measured using the Social Support Effectiveness-Questionnaire (SSE-Q) a 25-item version (Rini et al., 2011, J Consult Clin Psychol).

Participant Outreach and Contact: Study participants will be contacted at the following time points throughout the study:

1. Upon referral into the study. This contact will be from a member of the research team in order to conduct eligibility screening and review the study and next steps for consent and assessments
2. To schedule and/or conduct assessments by phone or REDCap survey link at baseline, post intervention, 3 and 6 months.
3. Text Messages after each session (MB +Text Only and FAB)
4. To check in with the study participants to make sure the study team has up to date contact information for the participant, as well as to stay engaged and build a rapport with the participant.
5. If the study participant is selected to participate in a focus group, research staff will call and coordinate focus group logistics.
6. Congratulation cards will be sent to each study participant after the birth of their baby
7. An information sheet will be mailed to notify participants who were previously consented and currently enrolled about the study being included in ClinicalTrials.gov and the change to the follow-up time points. We will only be following up at 6 months post-intervention and not at 9 month post-intervention.

5.0 Multiple sites: [name] is a CO-I on this grant. CO-I [name] is the developer of the text messages and HealthySMS platform. Since she will be overseeing the implementation of the text message platform she will have access to participant information. She will not be involved in the consent or follow-up procedures and will not be directly interacting with participants. [name]'s

Institution is Palo Alto University. Palo Alto's IRB is ceding IRB review to Northwestern and signed an IRB Authorization Agreement (IAA).

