During phase 2 of the study we will conduct focus groups with the identified 16 women from phase 1 of the study. We will also include their male partners (n=16) in two focus groups of 8 participants. All focus groups will only be held in English. Additionally we will recruit 36 women and their male partners (36 dyads from 10-12 HV programs) to participate in an uncontrolled pilot of the FAB intervention at two HV programs not participating in the Phase 1 RCT. We will conduct additional, qualitative data from 22 male partners after receiving FAB. Our informed consent from includes an option to be contacted for future research studies, we will only contact participants who indicate “yes” to this option for qualitative data collection activities (focus groups and key informant Interviews) after completing FAB.

Study Participants

Phase 1 (MB-TXT RCT)

We will recruit 108 study participants from 10-12 Home Visiting programs. English or Spanish-speaking women ≥ 16 years old enrolled in HV programs who are in their 1st or 2nd trimester (≤ 26 weeks) will be eligible for enrollment; across the 10-12 HV programs ~80% of women meet these criteria.

Phase 2 (FAB Development and Pilot)

(A) Focus Groups for FAB Development

We will recruit a total of 48 focus group participants, consisting of 16 female clients who participated in MB-TXT in Phase 1, 16 male partners of the female focus group participants, and 16 Home Visiting supervisors/managers and home visitors from the HV programs. The focus groups with the Home Visiting supervisors/managers and home visitors will be conducted during Phase 1 and 2 of the study. The focus groups will consist of 16 Home Visiting supervisors/managers and home visitors from the HV programs. The focus groups in phase 2 will consist of 16 female clients who participated in MB-TXT in Phase 1 and 16 male partners of the female focus group participants. All focus groups will only be held in English.

(B) FAB Pilot Study

We will recruit 36 women and their male partners (36 dyads from 8-10 HV programs). Eligible women (n=36) may be English speaking, ≥ 18 years old and enrolled in HV programs who are pregnant or

PROTOCOL TITLE: The Mothers and Babies Text Project

have a young child or children. Eligible men (n=36) may be English speaking, ≥ 18 years old, partners of female participants. We will recruit a total of 22 male partners who have received FAB (post-intervention) for focus group and key informant interviews.

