Home Visiting Programs

The 10-12 HV programs that use either the Healthy Families America (HFA) or Parents as Teachers (PAT) model. HFA and PAT are evidence-based⁷¹ paraprofessional HV models that enroll women prenatally and continue services until a child's second birthday (HFA) or entry into kindergarten (PAT). Both HFA and PAT recruit women at high risk for poor pregnancy and/or parenting outcomes via referrals from prenatal care clinics, community outreach, and current program participants. Both the HFA and PAT models call for weekly or bi-weekly home visits during pregnancy and the first six months postpartum. English or Spanish-speaking women ≥ 16 years old enrolled in HV programs who are pregnant will be eligible for enrollment in Phase 1 of the study. English speaking dyads; women ≥ 18 years old enrolled in HV programs and their male partners ≥ 18 years will be eligible for enrollment in Phase 2 of the study. Across the HV programs ~80% of women meet these criteria.

Vulnerable Populations

We will enroll pregnant women in both studies given that the Mothers and Babies Course can be delivered prenatally as a postpartum depression prevention intervention. In Phase 1, we will offer participation to pregnant women, ages 16 and older, knowing that the client population of HV programs is younger, on average, than the general population. In Phase 2, we will offer participation to pregnant women or have a young child or children who are enrolled in HV, ages 18 and older. Mothers and Babies has been used in similar HV settings in the state of Illinois and nationally, with high ratings of acceptability and usefulness and no ill effects of participation detected.

4.0 Procedures Involved:

Phase 1 (MB-TXT RCT)

Study Activities Include:

- Recruitment of participants for MB / MB + Text RCT
- Focus Groups with Home Visiting supervisors/managers and home visitors (2 Groups of 8, n=16)

Program Implementation (MB-TXT RCT)

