We will conduct a cluster RCT to determine the feasibility and acceptability of the MB-TXT intervention and calculate a preliminary effect size to determine a sample size for a future RCT. This RCT will also allow us to examine MB-TXT effects on proposed mechanisms underlying intervention efficacy. Cluster allocation by HV program minimizes contamination between study groups. We will work with 10-12 HV programs that have been trained on MB 1-on-1 and have working relationships with the PI. These programs provide a geographically, racially, and ethnically diverse set of recruitment sites. These programs are part of a network of Illinois HV programs overseen by the Illinois Governor's Office of Early Childhood Development which has supported scaling MB throughout Illinois and is enthusiastic about using text messaging to enhance intervention effectiveness. We will use a stepped wedge design—a form of RCT that involves sequential, but random, rollout of the intervention over multiple time periods. We have created two HV program clusters. Both clusters will initially implement MB 1-on-1 and will recruit MB participants for one quarter (i.e., three months) before crossing over to recruit MB-TXT participants for one quarter. MB-TXT's core curriculum is identical to MB 1-on-1 and adds a series of text messages throughout the curriculum.

Study Conditions:

MB 1-on-1. Half of our study participants (n=54) will receive MB 1-on-1. MB 1-on-1 is a manualized 12-session intervention divided into five modules. An introductory 2-session module establishes key

PROTOCOL TITLE: The Mothers and Babies Text Project

concepts related to stress, monitoring of one's mood, and ways in which one's mood influences one's internal thoughts and external environment; three 3-session modules correspond with key cognitive-behavioral elements: pleasant activities, thoughts, and social support/contact with others; a 1-session summary reviews content and identifies areas for future use of MB skills. Throughout MB, mood management skills are integrated using psycho-educational activities that encourage participants to understand connections between their mood and their activities, thoughts, and contacts with others. Content is tailored to specific needs and issues of pregnancy and the postpartum periods. Each MB session lasts 15-20 minutes and is delivered as part of a regularly scheduled home visit.

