6.0 Incomplete Disclosure or Deception: N/A

7.0 Recruitment:

Study Participants: During phase 1, we will recruit 108 study participants from each of the participating HV programs. We will enroll 108 HV clients at 10-12 HV programs, 54 women will receive Mothers and Babies 1-on-1 without text message enhancements and 54 women will receive Mothers and Babies 1-on-1 with text message enhancements. Of the 108 women, 16 will be recruited for focus groups phase 2 of the study.

During phase 2 of the study we will conduct focus groups with the identified 16 women from the 108 group that participated in phase 1 of the study. We will also include their male partners (n=16) in two focus groups of 8 participants. Additionally we will recruit 36 women and their male partners to participate in the FAB Pilot Study.

Home Visitors: We will recruit approximately 36 home visitors from 10-12 participating HV programs throughout the state of Illinois. All HV programs recruit women at high risk for poor pregnancy and/or parenting outcomes via referrals from prenatal care clinics, community outreach, and current program participation. All of the home-visitors who are being recruited through the participating home-visiting sites have been previous trained and are currently implementing Mothers and Babies 1-on-1. Home visitors that have not been trained will receive an in-person training (see training section for more detail). Each home-visitor will identify 1-4 client that will participate in study activities, of these clients 1-2 will receive MB without Text and 1-2 will receive MB with Text. All home-visitors will implement MB without text and MB with text. Programs will initially implement MB 1-on-1 and will recruit MB participants for six months before crossing over to recruit MB-TXT participants for 6 months. To pilot FAB 1-3 home-visitors from each program will identify 1-4 client dyads that will participate in FAB pilot study activities; Home-visitors who will implement FAB will recruit dyads.

We anticipate 16 home-visitors will participate in focus groups during phase 1 and 2 of the study. 10-12 HV programs will be recruited to implement the FAB pilot.

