Recruitment Procedures/Attrition: Recruitment procedures will be identical to those used in a previous RCT of MB in HV programs conducted by [name]. A postcard and/or flyer will be provided to the participating HV sites and the potential eligible study participants prior to NU research staff calling the study participants. The postcard/flyer will explain the purpose and overview of the study. Prior to beginning program implementation, potential study participants contact information will be obtained by the participating trained HV sites. The HV programs will fill out the referral form for eligible and interested participants, the form will be faxed or e-mailed to the Project Manager. The Project Manager and Research Assistant will share responsibility for calling each woman receiving HV services to tell them more about the recruitment and consenting process. A recruitment letter will be sent to the participants by the RA asking them to participate in the research study if the research team is unable to reach them by phone or email. The NU research team will also email the survey link to the study participants using email addresses provided by the HV sites, the link on NU REDCap database to be able to consent to participate in the program and complete a baseline assessment. The surveys will be available in both English and Spanish.

We will obtain names, phone numbers, and addresses of women and their partners. Individuals who meet our criteria for study eligibility but who are not interested in participating in our research activities will still be able to participate in the MB intervention. Based on previous research, we expect that fewer than 5% of eligible participants will opt out of research activities.

Phase 1 (MB-TXT RCT)

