8.0 Consent Process

All recruitment and consent procedures will be performed in accordance with guidelines of the Northwestern University Institutional Review Board. Women enrolling in home visiting programs during recruitment periods will complete the screening administered by phone by the Project Manager or Research Assistant. We request a waiver of written documentation of consent in order to administer this study online, or over the telephone if client participants do not have easy access to web-based resources. Online study implementation will decrease the time required to complete study assessments, and is more feasible to implement given that home visiting programs and clients across the State of Illinois and adjacent states will be participating, and our resources are limited.

Regardless of whether or not the study participant consents to the study online or over the phone, NU Research staff will offer the participant a copy of the consent form. If the study participant would like a copy of the consent, Research staff will either email or mail a copy of the consent form to the participant per their preferred method of contact.

Informed consent from home visiting participants and male partners will be collected primarily via a web-based survey using REDCap. For study participants who do not complete informed consent via REDCap, informed consent will be obtained by phone. Because in-person written consent will not take place, we will seek a waiver of documentation of consent from Northwestern University's Institutional Review Board. This protocol has been used successfully in prior HV studies conducted by [name].

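### Phase 1 does not settle whether women already on the home visiting caseload at launch are eligible; if they are, the MB-first order would place most of those recruited in MB, and no adjustment is planned

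*Combined protocol and SAP*

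**What the plan says.** Section 3.0 describes the Phase 1 population twice. Under Study Participants, women "enrolled in HV programs who are in their 1st or 2nd trimester (≤ 26 weeks) will be eligible for enrollment". Under Home Visiting Programs, "women ≥ 16 years old enrolled in HV programs who are pregnant will be eligible for enrollment in Phase 1 of the study", without the 26-week limit. Neither says when a woman must have joined HV.

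Section 7.0 (Recruitment Procedures/Attrition) says "Prior to beginning program implementation, potential study participants contact information will be obtained by the participating trained HV sites", and gives research staff the task of "calling each woman receiving HV services to tell them more about the recruitment and consenting process". The same section has programs complete referral forms for women who are eligible and interested. Section 8.0 says "Women enrolling in home visiting programs during recruitment periods will complete the screening administered by phone".

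On order, section 4.0 states "Both clusters will initially implement MB 1-on-1 and will recruit MB participants for one quarter", a quarter being three months, followed by one quarter of MB-TXT. Section 7.0 (Home Visitors) has programs "recruit MB participants for six months before crossing over to recruit MB-TXT participants for 6 months". It also has each home visitor identify one or two clients for each condition.

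For the analysis, sections 4.0 and 14.0 compare the arms at the individual level without adjusting for home visitor or program: t-tests for the BDI and Mann-Whitney tests for the mechanisms. Neither describes adjustment for time in HV or gestational age.

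**The concern.** When recruitment opens, a program has a standing caseload of pregnant clients. If they are eligible, the first window recruits from that stock plus new entrants. The second window recruits from new entrants plus whatever eligible stock the first window left. MB is first in both clusters, so staggering the clusters' start dates would not balance this.

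Women from the standing caseload have been in HV longer, know their home visitor better and are on average further into pregnancy. Each could plausibly relate to BDI change, homework completion or retention. An unadjusted two-sample test would read any resulting difference as an effect of the text messages. Aim 2 exists to supply an effect size for planning the next trial, so the error would carry forward.

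**Working it through.** **The plan's own figure.** Section 14.0 has 54 per arm with 15% attrition: 54 × 0.85 = 45.9, or 46. Power for an effect of 0.59, two-sided 5%, is 80.8% by normal approximation and 79.9% by noncentral t. For 0.52, one-sided, it is 80.2% and 79.7%. The stated 80% reproduces to rounding and is not in dispute. The standard error of the standardised difference is about √(2/46) = 0.21.

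**Timing, from the documents.** With a 26-week limit, a client at gestational age g at launch is still eligible at crossover only if g + 13 ≤ 26, so g ≤ 13 weeks, with three-month windows. With six-month windows, essentially none is.

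**Shares, on assumption.** The documents give neither the HV entry pattern nor caseload size. Assume a constant entry rate, with gestational age at entry uniform from 8 to 26 weeks. Mean remaining eligibility is (26 − 8)/2 = 9 weeks, so the stock equals 9 weeks of entries. The share already in HV when a window opens is:

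| Windows | MB | MB-TXT, all eligible recruited earlier | MB-TXT, half recruited | MB-TXT, few recruited |
|---|---|---|---|---|
| 3 months | 9/(9+13) = 41% | about 0% | 4.5/(4.5+13) = 26% | approaches 41% |
| 6 months | 9/(9+26) = 26% | about 0% | 4.5/(4.5+26) = 15% | approaches 26% |

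Starting entry at 6 or 12 weeks instead, with 95% uptake, women on the caseload at launch are about 35–43% of MB recruits and at most 0.5% of MB-TXT recruits (three-month windows), or 21–28% and 0% (six-month windows).

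**Without the 26-week limit.** Under section 3.0's other statement, assuming HV entry at weeks 6–36, about 38% of the launch caseload is still eligible after 13 weeks and about 6% after 26.

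**Gestational age, three-month windows.** Mean in the stock is 8 + (2/3 × 18) = 20 weeks; among new entrants it is 17. MB: 0.41 × 20 + 0.59 × 17 = 18.2 weeks. MB-TXT: 17.0 if all were recruited earlier; 0.26 × 20 + 0.74 × 17 = 17.8 if half were.

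**Bias.** Bias = (MB share − MB-TXT share) × D, where D is the difference in BDI change between existing and new clients. Assume D is 0 to 0.4 SD; the documents give no value.

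- Three-month windows, all recruited earlier: 0.41 × 0.4 = 0.16 SD. Half recruited: (0.41 − 0.26) × 0.4 = 0.06 SD.
- Six-month windows, all recruited earlier: 0.26 × 0.4 = 0.10 SD.
- Lower bound: 0, if D is 0 or if the first window takes only a small part of the eligible caseload.

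**Effect on the next trial.** Required sample size scales as 1/d². Taking 0.59 purely as an illustration, a 0.16 SD error changes it by a factor of (0.59/0.75)² = 0.62 or (0.59/0.43)² = 1.88.

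**The case against.** A reader might infer that the protocol sets out two opposed eligibility criteria. It does not. A woman enrolled in HV may be a new enrollee, and the section 8.0 sentence concerns phone screening within the consent process. The calling instruction in section 7.0 follows referral of eligible women and carries no gestational limit of its own, so it does not open the study to every current client. What stands is an ambiguity: contacts may be drawn before implementation, and nothing says whether the launch caseload is in or out.

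A reader might also infer that the imbalance tracks condition exactly. The documents do not support that. With three-month windows, women at 13 weeks or less at launch can carry over. One of section 3.0's two statements drops the limit altogether. One or two clients per home visitor per condition is closer to a quota than to recruitment of all comers, so a similar stock may remain at crossover. For the same reason no positive minimum bias can be claimed.

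Even 0.16 SD is below one standard error (0.21), and section 4.0 concedes that Aim 2 inference is limited by the pilot. That argues for proportion, but a systematic shift still moves the estimate in a way that sampling error does not describe.

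Nor can it be said that the two variables go uncollected. Gestational age is needed to apply the 26-week limit, and Table 1 lists 17 baseline demographic items and a service-utilization instrument whose contents are not shown.

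**Conclusion.** The point holds conditionally. The documents leave open whether launch-caseload women are eligible. If they are, MB-first order and the 26-week limit would put most of those recruited into MB, and the described analysis takes no account of time in HV or gestational age. The bias lies between 0 and about 0.16 SD with three-month windows, or 0 and about 0.10 SD with six-month windows, direction unknown, against a planned detectable effect of 0.59. These limits rest on the assumed entry pattern, the share recruited in the first window and an assumed 0–0.4 SD difference; none is a document figure. If only women joining HV during a window are eligible, this source of imbalance disappears. The broader confounding of condition with calendar period remains on either reading. For a pilot this merits correction because the remedy is cheap; it does not invalidate the design.

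**What to change.** 1. Reconcile both eligibility statements in section 3.0, the recruitment text in section 7.0 and the screening sentence in section 8.0 into one entry rule applied in both windows. Reconcile the three-month and six-month windows in sections 4.0 and 7.0.
2. Record HV start date and gestational age at referral or baseline, if not already captured, and report both by arm.
3. Adjust the BDI and mechanism comparisons for time in HV and gestational age. The planned two-sample tests take no covariates, so this means a regression alongside them.
4. Add an exploratory sensitivity analysis in women who entered HV during their own window. If long-standing clients fall almost wholly in MB, the adjustment leans on extrapolation, and this analysis avoids that.
5. State as a limitation that condition remains confounded with calendar period, which these steps do not remove.

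The cost is up to two form fields and two degrees of freedom. The sensitivity sample is smaller: in the 41% case about 46 × 0.59 = 27 in MB against 46 in MB-TXT, with a detectable effect of about 2.80 × √(1/27 + 1/46) = 0.68, and fewer women if MB-TXT also loses some. Restricting entry to new HV enrollees would also balance this feature, but could remove up to about 41% of the MB pool in the same model, so it is a trade-off to weigh rather than a cheap alternative.
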